10. PHARMACODYNAMICS (PD)

No PD analysis is planned for this study.

Pharmacokinetic/Pharmacodynamic analysis falls outside the scope of the SAP.

11. EFFICACY

No efficacy analysis is planned for this study.

12. SAFETY

Safety endpoints will be analyzed using the safety analysis set. All information will be presented by cohort and overall, by study part. All safety data will be listed by cohort and study part.

12.1 Adverse Events

12.1.1 Definition of variables

- AE
- Serious adverse event (SAE)
- Treatment emergent adverse event (TEAE)

AEs and SAEs are defined in the study protocol. TEAEs are defined as any AEs with an onset date of on or after the study drug start date and no later than 30 days after permanent discontinuation of study drug. Adverse events that have missing onset dates will be considered treatment-emergent, unless the stop date is known to be prior to the first administration of the study medication.

12.1.2 Biostatistical methods

All AEs including will be coded using MedDRA.

All AE summaries will be restricted to TEAEs only. Summary tables will include the number of subjects (%) experiencing an event and the number of events. Subjects will be counted only once at each SOC and PT level of summary.

The TEAE summaries will include:

- Overall Summary of TEAEs
- TEAE summary by SOC and PT
- TEAE summary of serious events by SOC and PT
- TEAE summary by causality to study drug by SOC and PT
- TEAE summary by maximum toxicity
- TEAE summary by SOC, PT and maximum toxicity

All SOC by PT tables will be sorted by PT in descending order of total occurrence for each part.

All AEs will be listed and will include verbatim term, PT, SOC, treatment, severity, relationship, seriousness, outcome, and action taken with regards to the study drug. Separatelistings will be created for AEs leading to study withdrawal and SAEs.

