1.3. Overall Risk/Benefit Assessment

This study will provide information on the safety, PK, and antiviral activity of VIR-2218, an siRNA therapeutic targeting HBV, which has the potential to functionally cure chronic HBV infection alone or in combination with other treatment modalities.

The potential benefits of VIR-2218 over the current standard of care for the treatment of chronic HBV infection are:

- A pangenotypic therapy for HBV infection that is well-tolerated and administered via SC injection for a finite duration of time
- A reduction in serum HBsAg, which may break immune tolerance against HBV and lead to a functional cure

The safety profile of VIR-2218 has not yet been established. CCI [REDACTED] CCI [REDACTED] To further mitigate risk, a “sentinel” dose design will be used in Part A as follows.

- Two subjects will be randomized 1:1 to VIR-2218 or placebo and dosed concurrently
- These subjects will be monitored for 24 hours and if the investigator has no safety concerns, the other subjects in the same cohort are dosed. The remaining 6 subjects will be randomized 5:1 to VIR-2218 or placebo.

During the conduct of the study, the Sponsor will perform ongoing safety reviews and the SRC will meet to review safety data.

In summary, there is no approved therapy that reduces serum HBsAg in a significant percentage of patients. If serum HBsAg can be effectively reduced with a pangenotypic regimen, the anticipated safety profile would offer a favorable risk-benefit determinant in patients with chronic HBV infection.

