4.6.2. Individual Subject Stopping Rules in Part B/C

Individual subjects in Part B/C who have received 1 dose of study drug will not receive a second dose if any the following criteria are met:

- Serum ALT > 10 × ULN
- Serum ALT > 5 × ULN, with no change (< 50% of baseline) in HBsAg
- Serum ALT or AST > 3 × ULN with a concomitant total bilirubin > 2 × ULN
- Any clinical manifestations of hepatic decompensation

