8.2.2. Assessment of Severity

AE severity should be graded using the CTCAE Version 5.0.

8.3. Investigator Requirements and Instructions for Reporting Adverse Events and Serious Adverse Events to Vir

Requirements for collection prior to study drug initiation:

After informed consent, but prior to initiation of study medication, the following types of events should be reported: AEs related to protocol-mandated procedures and all SAEs.

Adverse Events

Following initiation of study medication, collect all AEs, regardless of cause or relationship, until 12 weeks after last administration of study drug.

All AEs should be followed up until resolution or until the AE is stable, if possible. Vir may request that certain AEs be followed beyond the protocol-defined follow-up period.

Serious Adverse Events

All SAEs, regardless of cause or relationship, that occur after the subject first consents to participate in the study (ie, signing the informed consent) and throughout the duration of the study, including the protocol-required follow-up period, must be reported as instructed. This also includes any SAEs resulting from protocol-mandated procedures performed after informed consent is signed.

Investigators are not obligated to actively seek SAEs after the protocol-defined follow-up period. However, if the investigator learns of any SAEs that occur after study participation has concluded and the event is deemed relevant to the use of study drug, he/she should promptly document and report the event to Vir.

- For fatal or life-threatening events, copies of hospital case reports, discharge summaries, autopsy reports, and other documents should be submitted by email or fax when requested and applicable. Transmission of such documents should occur without personal subject identification, maintaining the traceability of a document to the subject identifiers.
- Additional information may be requested to ensure the timely completion of accurate safety reports.
- Any medications necessary for treatment of the SAE must be recorded onto the concomitant medication section of the subject's eCRF and the event description section of the SAE form.
- Email or fax the SAE form within 24 hours of the investigator's knowledge of the event. Contact information is as follows:

PPD

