9.5. Safety Analysis

All safety analyses will be performed using the Safety Analysis Set. Safety will be evaluated by assessment of clinical laboratory tests, physical examinations, ECGs, vital signs measurements at various timepoints during the study, and by the documentation of AEs.

All safety data collected up to 12 weeks after the last study drug administration will be summarized by cohort for each VIR-2218 dose and placebo.

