9.5.1. Adverse Events

Clinical and laboratory AEs will be coded using the Medical Dictionary for Regulatory Activities (MedDRA). System Organ Class (SOC), High-Level Group Term (HLGT), High-Level Term (HLT), Preferred Term (PT), and Lower-Level Term (LLT) will be attached to the clinical database.

Treatment-Emergent Adverse Events (TEAEs) are defined as any AEs with an onset date of on or after the study drug start date and no later than 30 days after permanent discontinuation of study drug.

Summaries (number and percentage of subjects) of TEAEs by SOC and PT will be provided by cohort. TEAEs will also be summarized by relationship to study drug and severity.

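### The SAP limits AE tables to a 30-day treatment-emergent window, although the protocol says safety data to 12 weeks after the last dose will be summarized by cohort

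*SAP*

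**What the plan says.** Four statements bear on this point.

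- **What is collected.** Protocol 8.3 instructs sites, once study drug has started, to "collect all AEs, regardless of cause or relationship, until 12 weeks after last administration of study drug".
- **What the protocol says will be summarized.** Protocol 9.5: "All safety data collected up to 12 weeks after the last study drug administration will be summarized by cohort". Protocol 9.5.1 then defines treatment-emergent adverse events (TEAEs) with a 30-day limit and adds: "Summaries (number and percentage of subjects) of TEAEs by SOC and PT will be provided by cohort". It also asks for TEAE summaries by relationship and severity. It does not say that AE summaries are confined to TEAEs.
- **What the SAP tabulates.** SAP 12.1.1 repeats the protocol's TEAE definition, with onset "no later than 30 days after permanent discontinuation of study drug". SAP 12.1.2 then says: "All AE summaries will be restricted to TEAEs only". Its list of tables, including the one for serious events, is under that restriction.
- **What happens to later AEs.** SAP 12.1.2: "All AEs will be listed and will include verbatim term, PT, SOC, treatment, severity, relationship, seriousness, outcome". There are also separate listings for SAEs and for AEs leading to withdrawal.

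SAP 15 declares no change to the planned analysis.

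**The concern.** Incidence of AEs is a primary endpoint in all three parts (Protocol 3.1 and 3.2; SAP 2.3.1), and it is worded in terms of AEs, not TEAEs. The SAP restriction means that an AE with onset after the 30-day cut, but within the 12-week collection period, enters no table. A listing shows the event with its treatment and seriousness. It does not give incidence by dose, or for placebo combined across cohorts as the protocol synopsis plans.

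The cut date is also unclear. Neither document says which date counts as permanent discontinuation. The gap is plainest for Part B/C subjects stopped under Protocol 4.6.2: "Individual subjects in Part B/C who have received 1 dose of study drug will not receive a second dose" if a criterion is met. For them the clock could start at the only dose or at the withheld Week 4 dose.

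The safety outputs would also cover different periods. SAP 12.2.1 summarizes laboratory results at every scheduled post-baseline visit, so a Week 12 laboratory value is tabulated while an AE starting at the same visit is not.

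**Working it through.** No sample-size or power formula applies. The check compares two windows by day arithmetic.

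**Inputs**
- Last dose: Day 1 in Part A; Week 4 (Day 29) in Part B/C (Protocol 4.1.1, 4.1.2).
- TEAE limit: 30 days (SAP 12.1.1; Protocol 9.5.1).
- Summary limit in Protocol 9.5: 12 weeks = 84 days after the last dose.
- Visit days and windows: Protocol Appendices 2 and 3.
- Assumption: discontinuation is dated to the last dose, unless stated otherwise.

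**Formulas**
- TEAE cut = last-dose day + 30.
- 12-week end = last-dose day + 84.
- Untabulated days = 12-week end − TEAE cut.

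| Group | TEAE cut | 12-week end | Untabulated days after dose |
|---|---|---|---|
| Part A | 1 + 30 = Day 31 | 1 + 84 = Day 85 | 85 − 31 = 54; 54/84 = 64.3% |
| Part B/C, two doses | 29 + 30 = Day 59 | 29 + 84 = Day 113 | 113 − 59 = 54; 54/84 = 64.3% |
| Part B/C, one dose, dated to Day 1 | Day 31 | Day 85 | 54; 54/84 = 64.3% |
| Part B/C, one dose, dated to withheld dose | Day 59 | Day 85 | 85 − 59 = 26; 26/84 = 31.0% |

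Day 85 and Day 113 are the nominal days of the Part A Week 12 and Part B/C Week 16 visits, so the schedules run to the 12-week limit. Counted from the first dose instead, the untabulated share for two-dose Part B/C subjects is 54/(113 − 1) = 54/112 = 48.2%.

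**Scheduled post-dose visits after the cut**
- Part A: Days 2 and 3 and Weeks 1, 2, 3, 4, 8 and 12 make 8 visits. Weeks 8 and 12 fall after Day 31: 2/8 = 25%. Visit windows do not change this (Week 4 at the latest is Day 31; Week 8 at the earliest is Day 50).
- Part B/C, two doses: Day 2, Weeks 1 to 8, and Weeks 12 and 16 make 11 visits. Weeks 12 and 16 fall after Day 59: 2/11 = 18.2%. If the second dose is given on Day 27 (cut Day 57) and Week 8 falls on Day 58 or 59, or the dose is on Day 28 (cut Day 58) and Week 8 on Day 59, the count is 3/11 = 27.3%.
- Part B/C, one dose: 10 visits to Week 12. Dated to Day 1, Weeks 5 to 8 and 12 fall after the cut: 5/10 = 50%. Dated to the withheld dose, only Week 12 does: 1/10 = 10%.

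**Weight of one subject.** In Part A, one of the two sentinels is active, and "The remaining 6 subjects will be randomized 5:1 to VIR-2218 or placebo", so a base cohort has 1 + 5 = 6 active subjects. One subject whose only AE is late changes incidence by 1/6 = 16.7 points. A Part B/C base cohort of 4 randomized 3:1 has 3 active subjects: 1/3 = 33.3 points. Both figures exclude floater subjects.

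**The case against.** The strongest reply is that the 30-day definition is the protocol's own, and that every AE summary named in Protocol 9.5.1 is a TEAE summary. On that reading the SAP follows the section specific to AEs, and the conflict lies inside the protocol, between 9.5 and 9.5.1. Part of this stands: the definition is shared. But the two sections are compatible, because TEAE tables plus a 12-week table would meet both. The word *only*, which the SAP adds, is what prevents that.

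Second, for subjects who complete the planned dosing, permanent discontinuation may have no date at all. SAP 5.1.1 counts treatment completion separately from reasons for treatment discontinuation. Read literally, the TEAE window then has no clear end for completers, and the untabulated share could be 0 of 84 days. This stands as a limit on the 64% figure. It is also a reason to define the term.

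Third, the practical effect may be small. Late AEs are listed, cohorts are small enough to count by hand, asymptomatic laboratory changes are tabulated separately, and nothing is tested. All true, but a listing is not the summary by cohort that Protocol 9.5 states. Visit counts are also only a rough guide, because an AE reported at a late visit may have started before the cut.

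Finally, the SAP mentions Parts D to F and stopping rules in a protocol Section 4.8, neither of which is in the supplied protocol. It may follow another version whose Section 9.5 reads differently. That cannot be settled from these documents.

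**Conclusion.** The concern holds. In the documents supplied, the SAP restricts every AE table to TEAEs and so does not deliver the 12-week summary by cohort in Protocol 9.5, and SAP 15 records no departure.

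With discontinuation dated to the last dose, AEs with onset after Day 31 in Part A, or after Day 59 in two-dose Part B/C subjects, are listed but not tabulated: 54 of the 84 days after the last dose. For one-dose Part B/C subjects the figure is 26 to 54 days, depending on the date used.

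The number of events affected cannot be derived. Placebo has the same cut, so the effect on the drug-placebo contrast depends on event timing, which the documents do not give. This should be fixed because it concerns how a primary endpoint is reported. It does not affect any test or the laboratory tables.

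**What to change.** 1. Keep the 30-day TEAE tables. Replace the restriction in SAP 12.1.2 with wording such as: *AE summaries will be produced for TEAEs and, separately, for all AEs and SAEs with onset from first dose through 12 weeks after the last dose* (overall, by SOC and PT, by causality, and by maximum grade). This meets both Protocol 9.5 and 9.5.1.
2. State in SAP 12.1.1 which date counts as permanent discontinuation, both for subjects who complete dosing and for Part B/C subjects given one dose.
3. If the tables are not added, reconcile Protocol 9.5 with 9.5.1, or record the departure in SAP 15.
4. Optional, and not needed to meet Protocol 9.5: show SAEs from the Part B/C extended follow-up after Week 16 in a separate table, with number of subjects and follow-up time per group. Do not pool them with the 12-week incidence, because entry to that period depends on HBsAg decline (Protocol Appendix 3, note c).

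The cost is a few tables and one definition; the data are already collected. Adding the tables needs no protocol change. Rewording Protocol 9.5 or 9.5.1 instead would need IRB or IEC submission (Protocol 10.1.10). Reported absolute AE rates may be higher in both the active and placebo groups.

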12.2 Safety Laboratory Assessments

Blood and urine samples will be collected at the time points specified in the schedule of events (refer to the Protocol) to conduct hematology, coagulation, chemistry and urinalysis analyses.

The following tests will be performed within each of the specified test panels:

Hematology:

- Complete blood count with differential

Chemistry:

- Albumin
- Creatinine clearance
- Blood urea nitrogen (BUN)
- Gamma glutamyl transferase (GGT)
- Calcium
- Glucose
- Carbon dioxide/bicarbonate
- Lactate dehydrogenase (LDH)
- Chloride
- Potassium
- Creatine kinase
- Sodium
- Creatinine
- Urea
- Uric acid
- Liver Function Tests
 - Alkaline phosphatase (ALP)
 - AST
 - ALT
 - Bilirubin (total and direct)

Coagulation:

- International normalized ratio (INR) time
- Prothrombin

Urinalysis & Microscopic Urinalysis:

- Specific gravity
- pH
- Glucose
- Proteins
- Red Blood Cells
- Ketones
- Bilirubin
- Urobilinogen
- Nitrite
- Leukocytes
- Visual inspection for appearance and color

- Microscopy (if clinically indicated)

12.2.1 Biostatistical Methods

All laboratory data collected at scheduled and unscheduled visits will be included in the listings, but only results collected as scheduled visits will be included in the summary tables.

Results for individual parameters may be reported in different units depending on the analyzing laboratory. If required, the results (and the corresponding normal range cut-off values) for individual parameters may be converted to International System of Units (S.I.) units to summarize the data.

For all the parameters where a unit value has been reported, the parameter names that will be used in the outputs will comprise of the test name and the unit of measure, for example, 'Albumin (g/L)'. Parameters will be sorted alphabetically within tables and listings.

For all parameters where a normal range limit value is reported, the normal range will be derived based on the available lower and upper limit values and any reported mathematical symbols. If both a lower and upper limit value is available, the normal range will be presented as '(Lower, Upper)'.

The reported results for each parameter with a defined normal range will be classified ('Low', 'or 'High') in relation to the defined normal range limits. If a result is equal to the normal range cut-off value, the result will be considered normal.

The change from baseline values at each post-baseline visit will be calculated for all parameters with continuous results.

The decimal precision to which the summaries for each parameter will be based on the maximum number of decimals to which the reported result or the normal range limits are presented to in the raw data. The results and normal ranges will be displayed to the same decimal precision in the listings.

The hematology and chemistry results tables will present summary statistics for each laboratory parameter within the specific test panel. For each parameter, summaries will be presented for the baseline and each scheduled post-baseline visit. In addition, summaries will be presented for the change from baseline values at each scheduled post-baseline visit.

Additionally, shift tables from baseline in CTCAE grade (version 5) from baseline will be summarized by counts and percentages along with a summary of maximum CTCAE Grade for post treatment lab assessments. The summary for the maximum CTCAE will be based on both scheduled and unscheduled visits.

The urinalysis table will present counts and percentages for the reported results at baseline and each post-baseline visit within each test parameter. Result categories will be ordered alphabetically, or in ascending order.

The listings of laboratory parameters will include all the information (fields) collected (including CTCAE derived values). In addition, the observations that are used as the baseline record (value) for each parameter will be flagged, and the change from baseline values at each post-baseline visit will be presented.

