Subjects enrolled in Part B/C of the study will remain outpatient. Subject screening will occur no more than 4 weeks prior to the Day 1 visit. Eligible subjects will undergo further assessments on Day 1 to qualify for study drug administration on Day 1. To exclude the presence of cirrhosis, screening will include a mandatory noninvasive assessment of liver fibrosis such as a FibroScan evaluation, unless the subject has results from a FibroScan evaluation performed within 6 months prior to screening or a liver biopsy performed within 1 year prior to screening that confirms the absence of Metavir F3 fibrosis or F4 cirrhosis.

Subjects in each cohort will be randomized 3:1 to receive VIR-2218 or placebo within 48 hours prior to study drug administration on Day 1. Subjects will return to the clinical investigative site at Week 4 to receive a second dose of the same study drug administered on Day 1. The decision to administer a second dose will be made based on Week 3 laboratory values in accordance with dose suspension/stopping criteria in Section 4.6.

CCI

Subjects will return to the clinical investigative site on an outpatient basis for safety, tolerability, PK, and antiviral activity monitoring at specified timepoints through the last Post-dose Follow-up Visit (Week 16). Additional HBsAg monitoring is required for subjects with HBsAg levels with a $> 10\%$ decrease from the Day 1 predose level at the Week 16 visit. Visits will occur

every 4 weeks starting at Week 20 up to Week 48 or until the HBsAg level returns to $\geq 90\%$ of the Day 1 predose level. Additional HBsAg monitoring may be discontinued at the Sponsor's discretion based on emerging data.

Based on review of the accumulated, available data in Parts A, B, and C, the SRC may recommend dosing of optional cohorts following the same stratification. In addition to the optional cohorts, a combined total of up to 16 "floater" subjects for Part B/C may be added to any cohort, as determined and approved by the SRC (see Section 4.5.5 and Appendix 6 for further information).

Fasting is not required for any study procedure/assessment. The assessments performed at each visit are described in Appendix 3 .

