Alcohol intake assessment ^g		X		X	X	X	X	X	X	X	X	X	X	X	X	X
Body weight	X															
Height and BMI	X															
Vital signs ^h	X	X	X	X	X	X	X	X	X	X	X	X	X			
Safety ECG ⁱ	X	X	X				X									
Pregnancy test ^j	X	X					X				X	X	X			
FibroScan ^k	X															
Screening viral serology ^l	X															
Laboratory assessments ^m	X	X	X	X	X	X	X	X	X	X	X	X	X	X ⁿ	X ⁿ	X ⁿ
Urinalysis ^m	X	X														

Part B/C																
Study Stage	Screening	Dosing Period						Post-dose Follow-up Period ^b						Extended Follow-up Period ^c		
Study Visit Week				W1	W2	W3	W4 ^a	W5	W6	W7	W8	W12	W16	W20	W24	
Study Visit Day ± Visit Window	D -28 to -1	D1 ^a	D2	D8 ±2	D15 ±2	D22 ±2	D29 ^a ±2	D36 ±2	D43 ±2	D50 ±2	D57 ±2	D85 ±7	D113 ±7/ET	D141 ±7	D169 ±7	Q28D ±7
Urine for drugs of abuse ^o	X															
Randomization		X														
Study drug administration ^p		X					X									
Blood samples for PK analysis ^q		X	X	X			X ^r	X								
Blood sample for HBsAg	X	X	X	X	X	X	X	X	X	X	X	X	X	X	X	X
Blood sample for anti-HBs	X										X		X		X	X ^s
Blood sample for HBeAg qualitative	X															
Blood sample for HBeAg quantitative for Part C only ^t		X					X				X	X	X		X	X ^s
Blood sample for anti-HBe for Part C only	X										X		X		X	X ^s
Blood sample for HBV DNA quantitation ^u	X	X					X				X	X	X	X	X	X ^s
CCI																

Part B/C																
Study Stage	Screening	Dosing Period						Post-dose Follow-up Period ^b						Extended Follow-up Period ^c		
Study Visit Week				W1	W2	W3	W4 ^a	W5	W6	W7	W8	W12	W16	W20	W24	
Study Visit Day ± Visit Window	D -28 to -1	D1 ^a	D2	D8 ±2	D15 ±2	D22 ±2	D29 ^a ±2	D36 ±2	D43 ±2	D50 ±2	D57 ±2	D85 ±7	D113 ±7/ET	D141 ±7	D169 ±7	Q28D ±7
CCI																
Review/Record AEs ^x	X															
Concomitant Medications	X															
NUC medication adherence	X															

AE = adverse event; ECG = electrocardiogram; ET=end of treatment; **CCI** HBeAg = hepatitis e-antigen; HBsAg = hepatitis B surface antigen; HBV = Hepatitis B Virus; NUC = nucleoside/nucleotide; PK = pharmacokinetics; MAD = multiple ascending dose

Note: When scheduled at the same timepoints, the assessments of vital signs and 12-lead ECGs must be performed first, before the physical examinations, blood sample collections, and urine collections.

^a Assessments performed predose unless otherwise specified.

^b If a subject withdraws prematurely from the study prior to their Week 16 visit, ET assessments should be performed.

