^c Additional HBsAg monitoring is required for subjects with HBsAg levels with a > 10% decrease from the Day 1 predose level at the Week 16 visit. Visits will occur every 4 weeks starting at Week 20 up to Week 48 or until the HBsAg level returns to ≥ 90% of the Day 1 predose level. For example, if Day 1 predose HBsAg is 560 IU/mL and Week 16 HBsAg is 490 IU/mL, the subject will be followed until HBsAg levels returns to ≥ 504 IU/mL. Additional HBsAg monitoring may be discontinued at the Sponsor’s discretion based on emerging data.

^d A complete medical history will be taken at screening including HBV genotype if available. Any changes should be updated prior to dosing.

^e Evaluation of inclusion criteria related to urine pregnancy testing and urine drug screen.

^f See Section 7.2.1 for assessments to be performed during a full physical examination.

^g Subjects’ alcohol intake will be recorded while on study.

^h Vital signs (blood pressure, pulse rate, respiratory rate, and temperature) should be measured in the supine position after the subject has rested comfortably for approximately 10 minutes. On Day 1, vital signs should be measured within 2 hours predose and 4 hours post-dose. On all other visit days, vital signs are only required to be recorded once during the visit.

ⁱ 12-lead safety ECGs will be recorded on the timepoints listed in Appendix 5 and should be measured in the supine position after the subject has rested comfortably for 10 minutes.

^j WOCBP are required to have pregnancy tests. A serum pregnancy test will be performed at screening and urine pregnancy tests will be performed thereafter. Negative pregnancy test must be confirmed prior to study drug administration.

^k Does not need to be performed if the subject has had a FibroScan in the 6 months prior to screening or liver biopsy in the year prior to screening that confirmed the absence of Metavir F3 fibrosis or F4 cirrhosis.

^l See Section 7.1.3 for viral serology parameters.

^m Clinical laboratory and urinalysis parameters are described in Section 7.2.8.

ⁿ Liver function tests only.

^o Drugs of abuse included in the screen are described in the inclusion/exclusion criteria. Screening results for drugs of abuse must be reviewed prior to dosing.

^p Study drug will be administered via SC injection as described in Section 6.2.4.

^q Blood samples for PK analysis will be collected at the timepoints listed in Appendix 5.

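### The SAP's maximum CTCAE grade summary drops the protocol's 12-week limit and, read literally, takes in Week 20–48 liver tests scheduled only for subjects whose HBsAg fell

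*SAP*

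**What the plan says.** - **SAP 12.2.1** plans shift tables in CTCAE grade "along with a summary of maximum CTCAE Grade for post treatment lab assessments". On which visits count, it adds: "The summary for the maximum CTCAE will be based on both scheduled and unscheduled visits". It gives no end date.
- **Protocol 9.5** does give one: "All safety data collected up to 12 weeks after the last study drug administration will be summarized by cohort".
- **SAP 15** (changes to the planned analysis) reports none.
- **Protocol Appendix 3, footnote c** defines who is followed after Week 16: "Additional HBsAg monitoring is required for subjects with HBsAg levels with a > 10% decrease from the Day 1 predose level", judged at the Week 16 visit. "Visits will occur every 4 weeks starting at Week 20 up to Week 48", or until HBsAg is back to at least 90% of the Day 1 value. The sponsor may also stop this monitoring early.
- **Protocol Appendix 3, footnote n** gives the laboratory panel at those visits: "Liver function tests only".

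**The concern.** A maximum can only stay the same or rise as results are added. If one group has more draws, it has more chances of a high grade even when the risk per draw is equal. Here the extra draws depend on a fall in HBsAg after randomization, which is the effect VIR-2218 is meant to produce. Length of laboratory follow-up is then a consequence of treatment response, and the arms are compared over unequal observation.

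The table matters. Laboratory results are part of the primary endpoint (Protocol 3.2). Protocol 8.1.1 and 8.1.3 generally keep laboratory abnormalities without symptoms or intervention out of the adverse event record, so a silent rise in ALT would be seen mainly in the grade tables.

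**Working it through.** **1. The plan's own count.** Part B: (3 + 2) cohorts × 4 = 20. Part C: (1 + 2) × 4 = 12. Floaters: 16. Total 20 + 12 + 16 = 48, as in Protocol 5.1. At 3:1 this is at most 36 on VIR-2218 and 12 on placebo.

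**2. Laboratory draws per subject.** The row "Laboratory assessments ^m" in Protocol Appendix 3 has post-baseline entries at Day 2, Weeks 1 to 8, Week 12 and Week 16: 1 + 8 + 2 = 11. The extended visits run from Week 20 to Week 48 every 4 weeks: (48 − 20)/4 + 1 = 8 at most. The ceiling is 11 + 8 = 19.

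**3. Where the Protocol 9.5 limit falls.** Protocol 4.1.2 fixes the last dose: "Subjects will return to the clinical investigative site at Week 4 to receive a second dose of the same study drug". Appendix 3 puts that visit at Day 29 ± 2. Adding 84 days gives a limit between Day 27 + 84 = 111 and Day 31 + 84 = 115. The earliest Week 20 visit is Day 141 − 7 = 134. None of the 8 extended visits falls inside the limit.

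Two boundary cases appear. The Week 16 visit is Day 113 ± 7, so it can be as late as Day 120 and fall after the limit while in window. A subject given only the first dose reaches the limit at Day 1 + 84 = 85.

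**4. Worst-case effect of reading the SAP alone.** Let p be the chance of a graded liver result at one draw, equal in both arms. The documents give no value, so p is assumed. With independent draws, P(at least one) = 1 − (1 − p)^k.

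| p (assumed) | k = 11 | k = 19 | gap (points) |
|---|---|---|---|
| 0.5% | 5.4% | 9.1% | 3.7 |
| 1% | 10.5% | 17.4% | 6.9 |
| 2% | 19.9% | 31.9% | 12.0 |
| 5% | 43.1% | 62.3% | 19.1 |

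The gap column is the difference between arms only if every VIR-2218 subject has all 8 extended visits and no placebo subject has any.

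**5. Partial extension in both arms.** Placebo subjects can meet the trigger by measurement variation alone. Assume no true change and a lognormal HBsAg measurement with coefficient of variation c. With s = √ln(1 + c²), P(trigger) = Φ(ln 0.9 / (s√2)). For c = 3%, 5%, 10% and 15% this is 0.6%, 6.8%, 22.8% and 30.9%, or 0.1, 0.8, 2.7 and 3.7 of 12 placebo subjects.

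If fractions qA and qP of the two arms are extended for all 8 visits, the gap is (qA − qP) × the gap in step 4. Assume qA = 90%:

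- p = 1%, qP = 7%: 0.83 × 6.92 = 5.7 points.
- p = 1%, qP = 23%: 0.67 × 6.92 = 4.6 points.
- p = 5%, same two cases: 15.9 and 12.8 points.

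**6. With the Protocol 9.5 limit applied.** Both arms have up to 11 scheduled draws, and the extended visits contribute a gap of 0.

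**The case against.** The strongest reply is that the plan already has an end date. Protocol 9.5 covers all safety data, the SAP does not withdraw it, and SAP 15 declares no change. Read together, the documents exclude every extended visit. This is right as far as it goes: a reader might infer that the plan as a whole has no cut-off, and that is not so. But tables are programmed from the SAP, and the SAP points the other way. It sets a 30-day window for treatment-emergent adverse events (12.1.1) and none for laboratory data. It counts 48-week follow-up as completion where relevant (5.1.1). It runs the final analysis after all subjects have finished (16.2), when Week 20–48 results will be in the database.

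Other tempting readings also go too far:

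- **That VIR-2218 subjects get 8 more draws than placebo.** The trigger is HBsAg, not arm. Some placebo subjects may be extended and some VIR-2218 subjects will not be. Eight is a ceiling per subject. That extended subjects will be mainly on VIR-2218 is plausible, but the documents give no figure.
- **That late liver tests exist only in extended subjects.** This holds for scheduled tests. Protocol 7.1 allows unscheduled visits in anyone.
- **That the outputs would conceal the missing late tests.** SAP 12.2.1 summarizes chemistry at each scheduled visit, and SAP 3.1 requires the number of non-missing values, so the by-visit tables would show it.

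The analysis is descriptive (SAP 3.3), so no error rate or power is affected. Numbers are small: one of 12 placebo subjects is 8.3 points, and results are shown by study part. This limits what any single table can prove, but readers will still compare the arms by eye. The table list in SAP 18 is blacked out, so a window stated there cannot be ruled out.

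**Conclusion.** The point holds as an inconsistency between SAP and protocol that can bias a primary-endpoint safety summary. It does not show that the plan, read as a whole, will produce the bias.

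If SAP 12.2.1 is followed literally, the active arm's maximum liver-test grade could be inflated with no hepatic effect. The 7–19 point range is a worst case. It assumes 100% against 0% extension for all 8 visits, independent draws, and a per-draw rate of 1–5%. Correlation between a subject's own results would shrink it. With 90% against 7–23% extended, also assumed, the gap is about 5–6 points at a 1% rate. Under Protocol 9.5 it is 0. The counts of 11, 8 and 19 draws and the Day 111–115 limit follow from the documents; the rates and extension fractions do not. Because the remedy is specific and nearly free, the change should be made.

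**What to change.** In SAP 12.2.1:

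1. State that the maximum-grade summary, and any shift table that uses a worst post-baseline grade, includes scheduled and unscheduled results up to 12 weeks after the last dose, per Protocol 9.5.
2. State how two cases are handled: a Week 16 visit that is in window but later than 84 days after the last dose, and a subject who received only one dose. A rule that simply says through Week 16 is not the same as the protocol limit.
3. Present Week 20–48 liver-test grades in a separate table for subjects in extended follow-up, by arm, with the number observed at each visit.

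If the sponsor does want later data in the maximum, SAP 15 should declare it as a departure from Protocol 9.5.

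The cost is SAP wording and one extra table. No data are dropped, and late liver signals stay visible.
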